12.3.4 Safety population

The safety population is defined as all participants in the enrolled population who received a study vaccination and had any safety data available. Participants in the safety population will be analyzed as "treated", i.e. according to the actual vaccine received at the first dose. All safety analyses will be performed using this population. The denominators for different safety endpoints may vary according to the number of participants with available data for the specific endpoint. For instance, the solicited systemic adverse event endpoints will be based only on those who have the corresponding CRF data regardless of other safety follow-up data.

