7.1 Analysis Populations

Definitions of analysis populations used are:

Enrolled Population: The enrolled population is defined as all screened participants who provide informed consent and are eligible for study participation, regardless of the participant's randomization and treatment status in the study.

Full Analysis (FA) population: The full analysis population is defined as all participants in the enrolled population who were randomized, received the first dose of the study vaccination, and provided at least one evaluable serum sample. The analysis based on this population will serve as supportive results for all immunogenicity objectives.

Participants in the FA population will be analyzed "as randomized", i.e. according to the vaccine a participant was designated to receive, which may be different from the vaccine that the participant actually received.

Per Protocol (PP) population: The per-protocol population is defined as all participants in the FA population who correctly received both study vaccines per randomization with no major protocol deviations that are determined to potentially interfere with the immunogenicity assessment of the study vaccines. This population will serve as the primary analysis population for all immunogenicity objectives. The criteria for exclusion of participants from the PP population is described in Section 10, Table A2, of this SAP.

Safety population: The safety population is defined as all participants in the enrolled population who received at least one dose of study vaccination and had any safety data available.

Participants in the safety population will be analyzed as “treated”, i.e. according to the actual vaccine received at the first dose. All safety analyses will be performed using this population. The denominators for different safety endpoints may vary according to the number of participants with available data for the specific endpoint. For instance, the solicited adverse event endpoints will be based only on those who have the corresponding CRF data regardless of other safety follow-up data.

The immunogenicity primary and secondary endpoints will be performed on the PP and FA population. Safety primary and secondary endpoints will be performed on the safety population. All other baseline and safety analyses, unless stated otherwise, will be performed on the safety population.

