7.4 Missing Data

In general, all missing data will be treated as missing completely at random and no imputation will be performed.

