12.2 Safety

The number and percentage of participants experiencing solicited post-vaccination reactogenicity (fever, diarrhea, vomiting, decreased appetite, irritability, decreased activity level) during the 7-day period after any dose will be tabulated by vaccine group and severity (Table 16). For the percentage within each group, an exact two-sided 95% CI will be provided using Clopper-Pearson method. The percentage of participants with at least one solicited post-vaccination reactogenicity between ROTAVIN and ROTAVIN-M1® groups after both doses and after each vaccination will be compared using a two-sided Fisher's Exact test with a significance level of 0.05. Results will be tabulated for the safety population for participants with available data. These results will be repeated after each dose (Tables 17 and 18) and are considered as supportive.

Solicited reactions will be presented by severity for each vaccine group after any vaccinations and after each vaccination (Figure 2-4).

Solicited reactions will be listed (Listing 11). Separate listings will be presented for solicited reactions ongoing on day 7 (Listing 12) and severe solicited reactions (Listing 13).

12. Secondary Analyses

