Mild	x (x), E	(xx.xx, xx.xx)	x (x), E	(xx.xx, xx.xx)	x (x), E	(xx.xx, xx.xx)	
Moderate	x (x), E	(xx.xx, xx.xx)	x (x), E	(xx.xx, xx.xx)	x (x), E	(xx.xx, xx.xx)	
Severe	x (x), E	(xx.xx, xx.xx)	x (x), E	(xx.xx, xx.xx)	x (x), E	(xx.xx, xx.xx)	
Irritability							
Total	x (x), E	(xx.xx, xx.xx)	x (x), E	(xx.xx, xx.xx)	x (x), E	(xx.xx, xx.xx)	
Mild	x (x), E	(xx.xx, xx.xx)	x (x), E	(xx.xx, xx.xx)	x (x), E	(xx.xx, xx.xx)	
Moderate	x (x), E	(xx.xx, xx.xx)	x (x), E	(xx.xx, xx.xx)	x (x), E	(xx.xx, xx.xx)	
Severe	x (x), E	(xx.xx, xx.xx)	x (x), E	(xx.xx, xx.xx)	x (x), E	(xx.xx, xx.xx)	
Decreased activity level							

	ROTAVIN N=XX		ROTAVIN-M1 N=XX		Total N=XX		p-value ^a
Total	x (x), E	(xx.xx, xx.xx)	x (x), E	(xx.xx, xx.xx)	x (x), E	(xx.xx, xx.xx)	
Mild	x (x), E	(xx.xx, xx.xx)	x (x), E	(xx.xx, xx.xx)	x (x), E	(xx.xx, xx.xx)	
Moderate	x (x), E	(xx.xx, xx.xx)	x (x), E	(xx.xx, xx.xx)	x (x), E	(xx.xx, xx.xx)	
Severe	x (x), E	(xx.xx, xx.xx)	x (x), E	(xx.xx, xx.xx)	x (x), E	(xx.xx, xx.xx)	

N= Total number of participants in the safety population in each vaccine group and overall.
n=Number of participants with non-missing values
x=Number of participants with a solicited reaction
E=Total number of solicited reactions
Percentages are based on the total number of participants in the safety population with non-missing values for at least one solicited adverse event in each vaccine group.
CI= Exact Confidence Interval using Clopper-Pearson
^ap-value is based on the Fisher exact test comparing ROTAVIN and ROTAVIN-M1

Table 17: Solicited Reactions – Safety Population – After Dose 1

{This table will be similar to Table 16}

Programming Note: E terminology will not be included in this table

Table 18: Solicited Reactions – Safety Population – After Dose 2

{This table will be similar to Table 16}

Programming Note: E terminology will not be included in this table

Table 19: Seroconversion for IgA at Day 85 – PP Population

	ROTAVIN	ROTAVIN-M1	Percentage Difference (95% CI ^b)
Number of observations	xx	xx	
x (%)	xx (xx.x)	xx (xx.x)	xx.x (xx.xx, xx.xx)
95% CI ^a	(xx.xx, xx.xx)	(xx.xx, xx.xx)	

N=Total number of participants in the PP population in each vaccine group

x=Number of participants who seroconverted

Percentages are based on the total number of participants in the PP population in each vaccine group.

^aCI= Exact Confidence Interval using Clopper-Pearson

^bCI of the difference in the percentage between the two vaccine groups from the Miettinen and Nurminen method

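### The solicited-reaction tables divide all six reaction rows by one common denominator, so an infant with no data on a reaction is counted as free of it

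*SAP*

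**What the plan says.** **The shells.** SAP 16.1, Table 16 (any dose) has a single participant-count row at the top, defined as "n=Number of participants with non-missing values". It has no count per reaction. The footnote then bases all percentages on safety-population infants "with non-missing values for at least one solicited adverse event in each vaccine group". Tables 17 (Dose 1) and 18 (Dose 2) have no shell of their own: "This table will be similar to Table 16". Table 62, on reactions ongoing at Day 7, carries the same footnote, and Tables 63 and 64 copy Table 62.

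**The text.** SAP 7.1 says: "The denominators for different safety endpoints may vary according to the number of participants with available data for the specific endpoint". Its example is that solicited endpoints are "based only on those who have the corresponding CRF data regardless of other safety follow-up data". Protocol 12.3.4 has the same rule: "the solicited systemic adverse event endpoints will be based only on those who have the corresponding CRF data". SAP 12.2 adds: "Results will be tabulated for the safety population for participants with available data". On gaps, SAP 7.4 says that "all missing data will be treated as missing completely at random and no imputation will be performed".

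**What is tested.** Under SAP 12.2 and Protocol 12.4.2, the Fisher comparison is on infants with at least one solicited reaction. The six single reactions are tabulated with Clopper-Pearson intervals and are not tested.

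**The concern.** One recorded value for one item puts an infant into the denominator of all six reactions. If that infant has no temperature data, fever cannot be counted, yet the infant still adds one to the fever denominator. In effect a missing item is read as no reaction. That is a form of imputation, in a display of the primary safety endpoint, in a plan that says it will not impute.

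The SAP uses item-specific denominators elsewhere. The Table 65 footnote bases heart-rate percentages on infants with a heart-rate value at that visit. Table 59 uses yet another wording for solicited data, namely vaccinated infants with the corresponding CRF data. A programmer will follow the footnote, so the footnote decides what is reported. At stake are the published rates and intervals for each of the six reactions.

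**Working it through.** **1. The plan's own figures.** Protocol 12.2 gives 550 and 275 infants, a 5% any-reaction rate on ROTAVIN-M1, a two-sided Fisher test at 0.05, and 90% power for a 6.8-point difference. Full enumeration of both binomials for 5% + 6.8% = 11.8% against 5% gives 90.8%. The other five rows of Table 12.2 give 90.7% to 91.0%. The detection statement also reproduces: 1 − (1 − 0.0055)^550 = 95.2%. These figures stand.

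**2. Effect of the common denominator on one row.** Let N be the infants in the common denominator, m the share with no data for the item, and p the true rate, with gaps unrelated to the reaction (the SAP 7.4 assumption).

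- Reactions that can be seen: p × N × (1 − m)
- Shown under the footnote: p × N × (1 − m) / N = p(1 − m)
- Shown with the row's own n: p × N × (1 − m) / [N × (1 − m)] = p

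Example with N = 550, m = 10%, p = 3%: 550 × 0.90 = 495 infants have data, and 0.03 × 495 = 14.85 events are expected. 14.85/550 = 2.70%, and 14.85/495 = 3.00%.

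The documents do not give m, so the range below is an assumption. The 3% is an upper figure for a single reaction: Protocol 2.5.3 reports that the commonest ones occurred in under 3% of ROTAVIN-M1 infants. The 5% and 11.8% are the plan's any-reaction rates, shown only for scale.

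| Assumed m | true 3% shown as | true 5% shown as | true 11.8% shown as |
|---|---|---|---|
| 0% | 3.00% | 5.00% | 11.80% |
| 1% | 2.97% | 4.95% | 11.68% |
| 2% | 2.94% | 4.90% | 11.56% |
| 5% | 2.85% | 4.75% | 11.21% |
| 10% | 2.70% | 4.50% | 10.62% |

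The Clopper-Pearson limits also fall, because the same event count is set against a larger n.

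**3. Effect on a comparison between arms.** With equal m in both arms the rate ratio is unchanged. If a row with 11.8% against 5% were tested, power under the common and the item-specific denominator would be 90.2% and 90.3% (m = 2%), 89.1% and 89.1% (5%), and 87.1% and 87.3% (10%). With gaps in one arm only and a true 5% in both, the spurious difference is 5% × m, which is 0.10 to 0.50 points for m of 2% to 10%. The detectable difference is 6.8 points.

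**4. Effect on the tested composite.** An infant lacking one item is misclassified only if every reaction that infant had fell in that item. For one item with rate 3% and no overlap with other reactions, the loss is at most m × 3%. That is 0.02 × 3 = 0.06 points to 0.10 × 3 = 0.30 points.

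**The case against.** Much can be said for leaving the footnote alone.

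- **SAP 7.1 is permissive.** It says denominators may vary, and its example refers to the corresponding CRF data. SAP 13.2.2 shows that all solicited reactions are entered on one reactogenicity form, so a form-level denominator is a natural reading, and the footnote roughly applies it. This stands. A reader might infer that the footnote contradicts SAP 7.1 outright. The text does not support that, because SAP 7.1 never says whether it means the form or the item.
- **Gaps may be rare.** Infants with no diary data at all are already excluded. Protocol 7.1 and 7.2 plan two home visits and a call after each dose to support completion, and Protocol 13.1 describes system checks for incomplete data. This stands too. A reader might infer that the primary safety rates are known to be too low, but the documents report no item-level missingness.
- **The tested row is a composite,** for which having at least one item recorded is a reasonable denominator. This stands.
- **A blank may mean no reaction.** If parents left items blank because the infant was well, the common denominator would be closer to the truth. However, Protocol 9.1 has the diary record presence or absence, and SAP 7.4 treats gaps as completely at random. On the plan's own terms a blank is missing.

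A further tempting inference concerns the any-dose table: that 10% of infants lack a Dose 2 diary and are counted as reaction-free after Dose 2. The 10% in Protocol 12.2 is a dropout allowance, not a rate of missing diaries. An infant never given Dose 2 has no Dose 2 reaction to miss. One who received it but has no diary would be a real gap, but the documents give no share for that, and Tables 17 and 18 report each dose separately.

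**Conclusion.** The point holds as a defect in the table shells. One denominator serves six reactions, and the row-level percentages and intervals are biased downward wherever an item is missing. It does not implement SAP 7.1's endpoint-specific principle, and it conflicts in effect with SAP 7.4.

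The size is a factor of (1 − m) on each single-reaction percentage. Under an assumed m of 2% to 10%, that is 0.06 to 0.30 points on a true 3% and 0.10 to 0.50 points on a true 5%. It is zero if no items are missing. The direction rests on gaps being unrelated to the reaction. The any-reaction comparison is little affected, and no stated power or sample-size figure changes. The case for acting is that the change costs almost nothing and removes a choice that could be questioned if it were made after unblinding.

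**What to change.** 1. In Tables 16 to 18 and 62 to 64, give each reaction row its own n: infants with at least one recorded value for that reaction in Days 1 to 7 after the dose. In the any-dose tables, use any dose received.
2. Use that n for the row's percentage and, in Tables 16 to 18, for its Clopper-Pearson interval.
3. Keep the current denominator for the row on at least one solicited reaction.
4. State in SAP 7.1 that the corresponding CRF data are the data for that item.

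The cost is a revised footnote, one extra n per row and slightly smaller row denominators. The per-row n also shows readers how complete each item was. A limit remains: an infant with one temperature reading and six blank days still counts as observed for fever. Repeating the any-reaction comparison in infants with complete diaries is optional. It would drop infants who had a recorded reaction and a single blank day, and so brings its own selection.

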18.	Did not meet I-E criteria but randomized	Participant met exclusion criterion	Participant met exclusion criterion 14: Clinically detectable significant congenital or genetic defect.	No PD review	Include
19.	Did not meet I-E criteria but randomized	Participant met exclusion criterion	Participant met exclusion criterion 15: History of persistent diarrhea (defined as diarrhea that lasts 14 days or longer).	No PD review	Exclude
20.	Did not meet I-E criteria but randomized	Participant met exclusion criterion	Participant met exclusion criterion 16: Receipt of immunoglobulin therapy and / or blood products since birth or planned administration during the study period.	No PD review	Exclude
21.	Did not meet I-E criteria but randomized	Participant met exclusion criterion	Participant met exclusion criterion 16: History of chronic administration (defined as more than 14 days) of immunosuppressants including corticosteroids. Infants on inhaled or topical steroids may	No PD review	Exclude

N	Protocol Deviation Category	Protocol Deviation Subcategory	Detailed Exclusion Description	PD Assessment	Decision for Per Protocol Population
			be permitted to participate in the study.		
22.	Did not meet I-E criteria but randomized	Participant met exclusion criterion	Participant met exclusion criterion 18: Any medical condition in the parents/LAR or infant that, in the judgment of the investigator, would interfere with or serves as a contraindication to protocol adherence	PD review	Decision will be taken on the case by case basis during the review of final protocol deviation listing performed prior to database lock
23.	Randomized to wrong treatment arm	Dosed with wrong treatment arm at visit 1	Received vaccine which is not as per randomization schedule generated for the study	No PD review	Exclude
24.	Wrong IP administered	Wrong vaccine of other arm administered at Dose 2	Due to wrong IP allocation, the participant received vaccine which is not as per randomization schedule generated for the study	No PD review	Exclude
25.	Wrong IP administered	Damaged / Expired / Quarantined IP used without prior approval	Participant received expired / damaged / quarantined vaccine	No PD review	Exclude
26.	Received Prohibited Medication /Vaccinations / Therapies	Receipt of blood products/ immunoglobulins outside the study center	Receipt of Prohibited Medication / immunoglobulin therapy and / or blood products during the study period.	No PD review	Exclude

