...	x (x), E	(xx.xx, xx.xx)	x (x), E	(xx.xx, xx.xx)	x (x), E	(xx.xx, xx.xx)	x (x), E	(xx.xx, xx.xx)	x (x), E	(xx.xx, xx.xx)	x (x), E	(xx.xx, xx.xx)	x (x), E	(xx.xx, xx.xx)	x (x), E	(xx.xx, xx.xx)	x (x), E	(xx.xx, xx.xx)	x (x), E	(xx.xx, xx.xx)
SOC 2	x (x), E	(xx.xx, xx.xx)	x (x), E	(xx.xx, xx.xx)	x (x), E	(xx.xx, xx.xx)	x (x), E	(xx.xx, xx.xx)	x (x), E	(xx.xx, xx.xx)	x (x), E	(xx.xx, xx.xx)	x (x), E	(xx.xx, xx.xx)	x (x), E	(xx.xx, xx.xx)	x (x), E	(xx.xx, xx.xx)	x (x), E	(xx.xx, xx.xx)
PT1	x (x), E	(xx.xx, xx.xx)	x (x), E	(xx.xx, xx.xx)	x (x), E	(xx.xx, xx.xx)	x (x), E	(xx.xx, xx.xx)	x (x), E	(xx.xx, xx.xx)	x (x), E	(xx.xx, xx.xx)	x (x), E	(xx.xx, xx.xx)	x (x), E	(xx.xx, xx.xx)	x (x), E	(xx.xx, xx.xx)	x (x), E	(xx.xx, xx.xx)
...																				

N=Total number of participants in the safety population

x=Number of participants with an unsolicited AE

E=Total number of unsolicited AEs

Percentages are based on the total number of participants in the safety population.

A participant may be counted in multiple rows within each system organ class; however, they will be counted only once in the overall row for the system organ class. Therefore, the sum of participants within each system organ class may not add up to the overall row for the system organ class.

A participant is only counted once per preferred term and is summarized according to their maximum severity.

All AE terms coded and reviewed on MedDRA version XX.X.

Programming Note: The SOCs will be ordered starting with the most common SOC.

Table 30: Unsolicited AEs within 4 weeks after each vaccination by System Organ Class, Preferred Term, Vaccine Group, and Severity – Safety Population – After Dose 1

{This table will be similar to Table 29}

Programming Note: The SOCs will be ordered starting with the most common SOC.
E terminology will not be included in this table

Table 31: Unsolicited AEs within 4 weeks after each vaccination by System Organ Class, Preferred Term, Vaccine Group, and Severity – Safety Population – After Dose 2

{This table will be similar to Table 29}

Programming Note: The SOCs will be ordered starting with the most common SOC.
E terminology will not be included in this table

Table 32: Unsolicited AEs within 4 weeks after each vaccination by System Organ Class, Preferred Term, Vaccine Group, and Relation with study vaccine – Safety Population – After Any Dose

MedDRA System Organ Class Preferred Term	ROTAVIN N=XX N (%)				ROTAVIN-M1 N=XX N (%)			

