Unknown/lost to follow up	x (x)	x (x)	x (x)	x (x)	x (x)	x (x)
Recovered/resolved without sequelae	x (x)	x (x)	x (x)	x (x)	x (x)	x (x)
Recovered/resolved with sequelae	x (x)	x (x)	x (x)	x (x)	x (x)	x (x)
Stabilized	x (x)	x (x)	x (x)	x (x)	x (x)	x (x)
Death	x (x)	x (x)	x (x)	x (x)	x (x)	x (x)
Total Deaths – After Any Dose	x (x)	x (x)	x (x)	x (x)	x (x)	x (x)
Relationship to Study Vaccine						
Related	x (x)	x (x)	x (x)	x (x)	x (x)	x (x)
Not related	x (x)	x (x)	x (x)	x (x)	x (x)	x (x)
Total Deaths – After Dose 1	x (x)	x (x)	x (x)	x (x)	x (x)	x (x)
Relationship to Study Vaccine						
Related	x (x)	x (x)	x (x)	x (x)	x (x)	x (x)
Not related	x (x)	x (x)	x (x)	x (x)	x (x)	x (x)
Total Deaths – After Dose 2	x (x)	x (x)	x (x)	x (x)	x (x)	x (x)
Relationship to Study Vaccine						
Related	x (x)	x (x)	x (x)	x (x)	x (x)	x (x)
Not related	x (x)	x (x)	x (x)	x (x)	x (x)	x (x)

	ROTAVIN x (%)	ROTAVIN-M1 x (%)	Total x (%)
x=Number of participants with an event			
^a Percentages are based on the total number of participants in the safety population in each vaccine group and overall.			
^b Percentages are based on the total number of events reported in each vaccine group and overall.			
^c Solicited reactions that become SAEs or that start within 30 minutes of vaccination are only counted as one event for the number of events.			
^d Percentages are based on the number of participants with available data.			
Participants may experience a given event multiple times during the study with differing severities and/or outcomes relation to IP; therefore, the sum of participants may not add up to the total row for the event.			
A participant may be counted in multiple rows for a given event if they experienced the event multiple times with differing severities or relation to IP; however, they will be counted only once in the overall row for that event. Therefore, the sum of participants may not add up to the overall row for the event.			

Table 58: Vaccination Administration – Safety Population

	Dose 1			Dose 2		
	ROTAVIN N=XX x (%)	ROTAVIN-M1 N=XX x (%)	Total N=XX x (%)	ROTAVIN N=XX x (%)	ROTAVIN-M1 N=XX x (%)	Total N=XX x (%)
Was vaccination given to the participant?						
Yes	x (x)	x (x)	x (x)	x (x)	x (x)	x (x)
No	x (x)	x (x)	x (x)	x (x)	x (x)	x (x)
Reason vaccination was not given						
Receipt of licensed rotavirus vaccine from outside	x (x)	x (x)	x (x)	x (x)	x (x)	x (x)
Reaction to an earlier dose of vaccine	x (x)	x (x)	x (x)	x (x)	x (x)	x (x)

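### The After Dose 2 tables for immediate AEs, unsolicited AEs and SAEs divide by the whole safety population, so infants never given Dose 2 dilute the rates

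*SAP*

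**What the plan says.** SAP 7.1 defines the safety population as enrolled infants who "received at least one dose of study vaccination and had any safety data available". Dose 2 is not a condition. The same section groups infants for every safety analysis "according to the actual vaccine received at the first dose", and adds: "The denominators for different safety endpoints may vary according to the number of participants with available data for the specific endpoint".

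In SAP 16.1, the After Any Dose shells for immediate AEs (Tables 23 and 26) and unsolicited AEs (Tables 29, 32 and 35) state "Percentages are based on the total number of participants in the safety population". The dose-specific tables are defined by reference to these shells. For Table 31 the instruction is "This table will be similar to Table 29", and the programming notes change only the SOC ordering and the event-count notation. The SAE tables (43–54) are in turn modelled on Tables 29, 32 and 35. No After Dose 2 table in these families names a Dose-2 denominator. For the participant columns of Table 57, footnote a says "Percentages are based on the total number of participants in the safety population in each vaccine group and overall".

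Solicited reactions are handled differently. The Table 16 shell, carried into Tables 17 and 18, uses "participants in the safety population with non-missing values for at least one solicited adverse event", and footnote d of Table 57 limits the solicited rows to infants with available data.

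**The concern.** Immediate and unsolicited AEs are secondary endpoints defined after each dose, so the After Dose 2 tables should describe risk among infants exposed to Dose 2. The documents foresee infants without it. Protocol 7.4 lets a parent decline further vaccination while safety follow-up continues. Protocol 5.1.3 lists events after which no further dose is given but the infant is still followed. SAP Tables 42 and 58 tabulate such infants. All of them stay in the safety population.

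If the shells are programmed as written, these infants add nothing to the numerator and a full count to the denominator. Rates and interval limits then come out too low, which is the unfavourable direction for a safety summary. The dilution would be unequal if the two groups differed in Dose-2 uptake.

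**Working it through.** **Inputs.**
- Arm sizes 550 and 275, and planned dropout 10% (SAP 5, Protocol 12.2).
- Exact Clopper-Pearson 95% intervals (SAP 13.2.1 to 13.2.3).
- Assumptions, because the plan gives no values: the share m of infants without Dose 2, the number of infants with an event, and a safety population equal to the full arm size.

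**The plan's own figure.** The plan states no Dose-2 AE rate. Its nearest binomial figure is the 95% probability of seeing at least one solicited reaction at a true incidence of 0.55% with 550 infants: 1 − (1 − 0.0055)^550 = 0.952. This reproduces and is not in dispute.

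**Tracing the denominator.**
- Tables 25 and 28 (immediate AEs) come from shells 23 and 26.
- Tables 31, 34, 37 and 40 (unsolicited AEs) come from shells 29, 32 and 35.
- Tables 45, 48, 51 and 54 (SAEs) come from the same three shells.
- In Table 57, the After Dose 2 participant rows for immediate AEs, unsolicited events, SAEs and deaths fall under footnote a.

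Each has the safety population as base. The Table 35 shell has no interval columns and Table 57 has none either, so intervals are affected only in Tables 25, 28, 31, 34, 45 and 48.

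**Formula.** With x infants having an event, N in the safety population and N₂ = N(1 − m) given Dose 2, the shell prints x/N where the rate among those exposed is x/N₂. The ratio is N₂/N = 1 − m, so the relative understatement equals m.

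**Liquid arm (N = 550, N₂ taken as a whole number).**

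| m | N₂ | x | Printed, x/550 | Among Dose-2 recipients, x/N₂ |
|---|---|---|---|---|
| 1% | 544 | 27 | 4.91% (3.26–7.06) | 4.96% (3.30–7.14) |
| 2% | 539 | 27 | 4.91% (3.26–7.06) | 5.01% (3.33–7.20) |
| 5% | 522 | 26 | 4.73% (3.11–6.85) | 4.98% (3.28–7.21) |
| 10% | 495 | 25 | 4.55% (2.96–6.64) | 5.05% (3.29–7.37) |
| 10% | 495 | 50 | 9.09% (6.82–11.81) | 10.10% (7.59–13.10) |

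With no events the upper limit is 1 − 0.025^(1/n), which gives 0.67% for n = 550 and 0.74% for n = 495.

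**Frozen arm (N = 275; N₂ = 248 at m = 10%).** Twelve events print as 4.36% (2.27–7.50) against 4.84% (2.52–8.30). The zero-event upper limit is 1.33% against 1.48%.

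**Unequal uptake, for illustration only.** If 10% lacked Dose 2 in one arm and 2% in the other, equal true rates of 5%, 10% and 20% would print with a gap of rate × (0.98 − 0.90), that is 0.4, 0.8 and 1.6 points.

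**The case against.** The best defence is that SAP 7.1 and Protocol 12.3.4 already let denominators follow the data available for an endpoint, and an infant without Dose 2 has no data for an after-Dose-2 endpoint. The quoted footnotes sit on After Any Dose shells, where the safety population is the right base, and the SAP presents its shells as templates. The summaries are descriptive, with no test attached. Protocol 7.4 expects few withdrawals. Dose-2 recipients are counted in Tables 1 and 57, so a reader could recompute a rate.

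Much of this stands as to size. It does not settle the denominator. The sentence in 7.1 is permissive and takes solicited events as its example, whereas the footnotes state one fixed base. Where the SAP wants a restriction it writes it into the shell: Tables 16–18 and 59–64, the vital-sign tables (65–70), Table 71 and footnote d of Table 57 all do so. The AE and SAE shells do not, and programmers work from shells. At the least, footnote and body text sit poorly together.

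A reader might infer two stronger points.
- **That every After Dose 2 safety measure is affected, including the primary safety endpoint.** It is not. Table 18 and the solicited rows of Table 57 use infants with data.
- **That the first-dose grouping rule is an error**, because Table A2 row 24 foresees "Wrong vaccine of other arm administered at Dose 2" and that infant's Dose-2 events count under the first-dose vaccine. The rule is explicit and the same in both documents. Regrouping by dose would put one infant in different arms in different tables and break agreement with the any-dose counts. Very few infants should be concerned, and they already have a row in Table 7 and appear in Listing 5.

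**Conclusion.** The point holds for Tables 25, 28, 31, 34, 37, 40, 45, 48, 51 and 54 and the non-solicited After Dose 2 participant rows of Table 57. Followed as written, the shells understate the Dose-2 rate by the fraction of the safety population not given Dose 2.

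The 10% case puts the whole planned dropout before Dose 2 and is an upper-end assumption. At a true rate near 5% it costs about half a percentage point. With 1–2% missing, the cost is 0.05–0.1 points, and if every infant receives Dose 2 it is zero. A reader might go on to infer a spurious difference between the vaccines. That needs unequal uptake, which nothing in the documents suggests. The immunogenicity analyses are untouched. This is a modest flaw in descriptive safety tables, worth correcting because its direction is favourable to the vaccines and the correction is nearly free.

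**What to change.** Change the SAP shells only.
- In the ten tables named above and the non-solicited After Dose 2 participant rows of Table 57, define N and the percentage base as safety-population participants who received Dose 2.
- Leave the available-data rule in Tables 16–18 and 59–64 and in the solicited rows of Table 57 unchanged. A blanket instruction for every After Dose 2 table would overwrite it and bring infants without diary data into the denominator.
- Keep the first-dose as-treated grouping. Optionally, flag in a listing any infant whose two doses differed.

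The cost is that N will differ between the Dose 1 and Dose 2 tables and the Dose-2 percentages become slightly less favourable. Because the grouping rule stays as it is, the protocol text needs no change.
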